**Table 3 – Censoring Rules for Progression-Free Survival**

Situation	End Date	Censored
Documented radiological PD	Date of the first tumor assessment that determined PD	No
Death during the study before PD	Date of death	No
Treatment discontinuation for other than radiologic PD or death with no post-baseline tumor assessments	Date of randomization	Yes
Treatment discontinuation for other than radiologic PD or death with post-baseline tumor assessments	Date of last adequate tumor assessment prior to initiation of non-study anti-cancer treatment	Yes
Patients still followed without radiologic PD as of cut-off date	Date of last adequate tumor assessment prior to cut-off date	Yes
Non-study anti-cancer treatment initiated before radiologic PD	Date of last adequate tumor assessment prior to initiation of non-study anti-cancer treatment	Yes
Death or radiologic PD after a missed (or not available/not evaluable) tumor assessment	
Date of last adequate tumor assessment prior to missed tumor assessment
 
A response assessment is considered “missed” if more than 13 weeks (91 days) has elapsed since the last image-based response assessment. If a patient develops progressive disease or dies after this interval, the tumor response assessment will be excluded from the analysis and censored at the last evaluable assessment. However, if a response assigned as CR, PR, or SD is obtained after more than 13 weeks, then the tumor response assessment will not be excluded from the analysis as long as no other censoring events have occurred.
 
Note: If patient dies within the 13 weeks from the last non-PD tumor assessment, death will be counted as a PFS event
	Yes

	unless the non-study anti-cancer treatment is initiated.	
Only non-evaluable (NE) tumor assessments after CR, PR, or SD	Date of last adequate tumor assessment prior to NE tumor assessments	Yes
No baseline tumor assessment	Date of randomization	Yes

General Considerations:
 
Tumor response assessment dates will be assigned based on the date the image was performed, not the date the image was assessed.
		

**Note:** Tumor response assessments will be considered “adequate” for analysis if they are assigned as CR, PR, SD, or PD and are not censored (e.g., obtained within 13 weeks since the last assessment and prior to initiation of non-study anti-cancer treatment: systemic anti-cancer therapy, radiotherapy or cancer surgery).

Tumor response assessments obtained after initiation of non-study anti-cancer treatment will not be included in the efficacy analyses, but will be flagged in the data listings. Tumor response assessments obtained the same day as initiation of non-study anti-cancer treatment will not be excluded.

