⁵ **The physical exam, vital signs determination, weight, performance status, laboratory evaluations (hematology, serum chemistry, and coagulation)** will be obtained within 1 day before study drug administration on Day 1 of each cycle. After Cycle 4, the Day 15 laboratory evaluations are not required unless clinically indicated by the investigator. After Cycle 6, the laboratory evaluations can be accepted within 2 days before study drug administration on Day 1 of each cycle, if there are no drug-related AEs greater than Grade 2 observed in the latest cycle.

⁶ **Pregnancy Test:** Pregnancy test is required at Baseline (within 7 days prior to Day 1 of Cycle 1) and at End of Treatment and 30-day Safety Follow-up visit. More frequent pregnancy assessments may be performed as required by local law.

⁷ **Concomitant medications** will be collected from the time of signing of the ICF through 30 days after administration of the last dose of study drug or until the start of new antitumor therapy, whichever is earlier.

AE/toxicity assessments will be collected from the time a patient starts receiving study treatment through 30 days after administration of the last dose of study drug or until the start of new antitumor therapy, whichever is earlier.

⁸ **Tumor assessments/scans** will be performed at baseline, at the end of every 6 weeks (± 7 days) beginning at Cycle 2 throughout all the treatment cycles, and at the time of discontinuation. See [Section 11.12](#), Tumor Assessments/Scans for details. Computerized tomography (CT) scans obtained before signing the ICF may be used as the baseline tumor scan if it is within 28 days of the first study drug administration. If the patient has discontinued treatment for reasons other than radiologic disease progression, a CT scan should be performed every 6 weeks (± 1 week) until the patient starts new anticancer therapy visit. Following Cycle 6, CT assessments may be adjusted to every 9 weeks.

⁹ **TAS-114 administration:** orally BID together with S-1 on Days 1 through 14 of each cycle. See [Section 9.1.2.1](#) for TAS-114 Dose Levels.

¹⁰ **S-1 administration:** orally BID together with TAS-114 on Days 1 through 14 of each cycle.

CCI [Redacted]

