14.1.2.1. Primary Efficacy Analysis

14.1.2.1.1. Progression Free Survival

PFS is defined as the time from the day of randomization to the start of disease progression or death (any cause), whichever occurs first, based on the blinded radiological review assessment of response. Patients who do not have disease progression or have not died will be censored at the last known time that the patient was progression free.

PFS in the efficacy population will be compared between the 2 treatment groups using the stratified log-rank test with significance level of one-sided 5%. PD events assessed by the central independent review will be used for primary efficacy analysis. The estimate of the hazard ratio and corresponding 90% and 95% confidence interval (CI) will be provided using a Cox proportional hazards (CPH) model including treatment and the 2 stratifications factors in the model. The survival curves will be estimated using the Kaplan-Meier method. The primary analysis for PFS will be conducted after 60 events have been observed based on independent assessment or after all patients have been followed for at least 3 months, whichever is later.

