### 3.5 Sample Size

The planned sample size is approximately 124 advanced or metastatic NSCLC patients. The study is designed to differentiate 4.2 months median PFS of treatment with TAS-114/S-1 from 2.2 months median PFS of treatment with S-1 (hazard ratio of 0.524) with 80% statistical power and a 1-sided type 1 error of 0.05. Using a treatment allocation of 1:1 (TAS-114/S-1: S-1), a target of 60 events (PD or deaths) will be required for the primary analysis, which corresponds to 71 events based on investigator review under the assumption that the discrepancy in PD events between the independent central review and investigator review is 15%. A total sample size of 124 patients is planned from the assumption that accrual period is 10 months, the percentage of PFS events is 65%, and the percentage of patients lost to tumor follow-up caused by study discontinuation is 10%.

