**Table 4 – Censoring Rules for Duration of Response**

Situation	End Date	Censored
Documented radiological PD	Date of the first tumor assessment that determined PD	No
Death during the study before PD	Date of death	No
Patients still followed without radiologic PD as of cut-off date	Date of last adequate tumor assessment prior to cut-off date	Yes
Non-study anti-cancer treatment initiated before radiologic PD	Date of last adequate tumor assessment prior to initiation of non-study anti-cancer treatment	Yes
Death or radiologic PD after a missed (or not available/not evaluable) tumor assessment	Date of last adequate tumor assessment prior to missed tumor assessment  A response assessment is considered missed if more than 13 weeks (91 days) has elapsed since the last image-based response assessment. If a patient develops progressive disease or dies after this interval, the tumor response assessment will be excluded from the analysis and censored at the last evaluable assessment. However, if an adequate image-based response assigned as CR, PR, or SD is obtained after more than 13 weeks, then the tumor response assessment will not be excluded from the analysis as long as no other censoring events have occurred.	Yes
Only non-evaluable (NE) tumor assessments after CR or PR	Date of last adequate tumor assessment prior to NE tumor assessments	Yes
General Considerations:  Tumor response assessment dates will be assigned based on the date the image was performed, not the date the image was assessed.		

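### SAP Table 3 gives two answers, with no stated precedence, for patients who stop treatment without radiologic PD and then progress or die before new therapy

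*SAP*

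**What the plan says.** - **Protocol 14.1.2.1.1:** "PFS is defined as the time from the day of randomization to the start of disease progression or death (any cause), whichever occurs first", by blinded central review. Only patients without progression or death are censored. Stopping treatment is not a ground for censoring.
- **SAP 6.2.1, text:** the same definition and limit, except that the last progression-free time must precede new anti-cancer treatment. A further sentence censors patients with no post-baseline disease assessment at randomization.
- **SAP Table 3, events:** row 1 (documented radiological PD) and row 2 (death before PD). Neither requires the patient to be on treatment.
- **SAP Table 3, discontinuation rows:** row 3 covers stops for other reasons with no post-baseline scan, censored at randomization. Row 4 reads "Treatment discontinuation for other than radiologic PD or death with post-baseline tumor assessments", censored at the last adequate assessment before non-study therapy.
- **SAP Table 3, note:** assessments are adequate "if they are assigned as CR, PR, SD, or PD and are not censored".
- **SAP Table 4 (duration of response):** PD is an event on the "Date of the first tumor assessment that determined PD". There is no discontinuation row.
- **Scans after stopping without radiologic PD:** for the combination arm, Protocol Table 1 footnote 8 says "a CT scan should be performed every 6 weeks (± 1 week) until the patient starts new anticancer therapy visit". For the S-1 arm, Table 2 footnote 8 asks for one CT within 2 weeks of the End of Treatment visit. Protocol 11.12 also asks sites to keep trying to document progression after treatment stops.
- **SAP section 8:** the only listed change from the protocol is an added time-to-treatment-failure analysis.

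**The concern.** A patient who stops for toxicity, at own request or for clinical progression, and whose later scan shows central PD before any new therapy, fits both row 1 and row 4. One row gives an event and the other a censored time, so two programmers could build different primary datasets from the same table. The protocol schedules scans to find exactly this progression.

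If row 4 were applied, events would be lost from the primary endpoint. Some of the loss would probably be informative: clinical progression is a listed reason for stopping (Protocol 8.3.1), and those patients are likely to be close to radiologic PD. If non-PD stops differ between the arms of this open-label trial, the hazard ratio shifts.

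**Working it through.** **1. Stop with scans, then central PD before new therapy**

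| Source | Result |
|---|---|
| Protocol 14.1.2.1.1 | Event |
| SAP 6.2.1, text | Event |
| Table 3, row 1 | Event at the PD scan |
| Table 3, row 4 | Censored at the last adequate scan before new therapy |
| Table 4, if a responder | Event ending the response |

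Row 4's end date runs to the start of new therapy, and an adequate scan may be a PD scan. Read literally, row 4 can therefore censor the patient on the day of progression. Rows 5 and 6 are explicitly limited to patients without PD, or without PD yet. Row 4 has no such limit.

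**2. Does row 1 prevail by default?** That cannot be assumed. Row 6 (new therapy before PD) and row 7 (PD or death after a gap of more than 13 weeks) both turn a documented PD into a censored time, so some later rows do override row 1.

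**3. Stop with no post-baseline scan, then death.** Row 2 gives an event at death, and row 3 gives censoring at randomization. The 6.2.1 definition and its main censoring sentence side with row 2. Its closing sentence on patients with no post-baseline assessment lacks the same condition as row 3.

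**4. Design figures.** The design (SAP 3.5) is 1:1, hazard ratio 0.524, "with 80% statistical power and a 1-sided type 1 error of 0.05".
- Schoenfeld events: 4 × (1.645 + 0.842)² / (ln 0.524)² = 59.2, so 60 as stated.
- Investigator events: 60 / 0.85 = 70.6, so 71 as stated.
- Patients: 71 / 0.65 / 0.90 = 121.4, so 122, close to the stated 124.

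No stated figure is wrong, and the fix changes none of them.

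**5. Event loss.** On the plan's assumptions, expected central events are 124 × 0.90 × 0.65 × 0.85 = 61.7, a margin of 1.7 over the target. The shares below are assumed.

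| Share of events removed | Events left | Power if analysis is not delayed |
|---|---|---|
| 0% | 61.7 | 0.814 |
| 5% | 58.6 | 0.796 |
| 10% | 55.5 | 0.777 |
| 20% | 49.3 | 0.734 |
| 30% | 43.2 | 0.684 |

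The analysis waits for the later of 60 events and 3 months' follow-up of all patients (SAP 7.5.1), so the loss may cause delay instead.

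**6. Bias under a true hazard ratio of 1.** Two simulations were run, both with 62 per arm, exponential PFS and 6-weekly scans.

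*Simulation A* (800 runs; 10 months' accrual plus 3; half of non-PD stops start new therapy; PD censored on the PD date):
- Stops of 20% on TAS-114/S-1 against 10% on S-1: mean hazard ratio 0.99 when these PDs count and 0.92 when censored; one-sided rejection 3.9% and 8.6%.
- Stops of 30% against 15%: hazard ratio 0.99 and 0.88; rejection 4.9% and 12.6%.
- Stops of 10% in both arms: no bias, about 5 events lost.

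*Simulation B* (1,500 runs; median 2.2 months; follow-up 3 to 13 months; the share is of patients whose PD is removed, censored at the preceding scan):

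| TAS-114/S-1 vs S-1 | Type I error | Median hazard ratio | Mean events |
|---|---|---|---|
| 0% vs 0% | 0.053 | 0.99 | 105.9 |
| 10% vs 10% | 0.054 | 1.00 | 95.2 |
| 20% vs 10% | 0.107 | 0.885 | 90.0 |
| 30% vs 10% | 0.210 | 0.788 | 84.4 |
| 10% vs 20% | 0.018 | 1.122 | 89.9 |

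Monte Carlo standard error at 5% is √(0.05 × 0.95 / 800) = 0.008 for A and √(0.05 × 0.95 / 1500) = 0.006 for B. The share means different things in A and B, so they agree on direction and rough size only. Neither models the arm difference in off-treatment scans. B also omits loss to follow-up and central-review discrepancy, which is one reason its event counts exceed 61.7.

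**The case against.** A reader might infer that the SAP lays down censoring of every off-treatment PD. The documents do not support that. Row 1 has no on-treatment condition, and the 6.2.1 text censors patients without progression or death. Row 4's end date reaches past treatment stop to new therapy, and the row 7 note counts a death within 13 weeks of the last non-PD scan unless new therapy has begun. Censoring on the day of progression is an odd enough result to suggest that row 4 was meant for patients without an event. A careful programmer may well count these PDs. This stands, and it makes the defect an unresolved conflict, not a stated rule.

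A reader might also infer that the error favours TAS-114/S-1. That does not follow. The stop shares are unknown, clinical-progression stops fall in the same row, and the reversed imbalance makes the test conservative.

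Other limits also stand. The affected group is narrow, because PD after new therapy or after a gap of more than 91 days is censored anyway. Table 4 is a shorter table, so its missing row is weak evidence of intent. Parts of SAP 7.5.1 are redacted and the Appendix 2 code is not visible, so a precedence rule or sensitivity analysis may exist there. A sensitivity analysis would not settle the primary rule.

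**Conclusion.** The conflict is real and concerns the primary endpoint. Rows 1 and 4 clash for PD after a non-PD stop, and rows 2 and 3 clash for death after a stop with no post-baseline scan. Nothing visible says which prevails. Applied literally, rows 3 and 4 contradict the definitions in Protocol 14.1.2.1.1 and SAP 6.2.1, row 4 is inconsistent with Table 4, and section 8 does not declare the departure.

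The harm is conditional on the literal rows being programmed. Equal shares in the two arms cost events with little or no bias. Unequal shares bias the comparison either way: one-sided type I error is about 0.09 to 0.11 at an assumed 20% on TAS-114/S-1 against 10% on S-1, and about 0.02 at 10% against 20% (simulation B only). These sizes illustrate the mechanism and are not forecasts. Both simulations address the row 4 conflict; the row 3 conflict was not sized.

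**What to change.** 1. Add to rows 3 and 4 of Table 3: *and no radiologic PD or death before non-study anti-cancer treatment*. Put the same condition on the 6.2.1 sentence about patients with no post-baseline assessment.
2. State that central PD or death after stopping treatment but before non-study therapy is an event at the scan or death date, subject to the existing 13-week missed-assessment rule. Without that proviso the new sentence would conflict with row 7. Say how the 13 weeks run when the baseline scan is the only one.
3. If censoring at discontinuation is intended, declare it in SAP section 8 and add a sensitivity analysis that counts these events, unless the redacted text already has one.

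The cost is two table rows and a few sentences before database lock, with no new data and no change to the 60 events or 124 patients. After lock, the rule actually used should be identified in the clinical study report, as section 8 provides.

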## 6.2.2 Secondary Efficacy Variables

### 6.2.2.1 Overall Survival

Overall survival (OS) in months is defined as the time from the day of randomization to death from any cause:  $(\text{date of death} - \text{date of randomization} + 1) / 30.4375$ . Patients who were alive at the end of study will be censored at the last date the patient is known to be alive. Patients without post-baseline information will be censored at the time of randomization.

### 6.2.2.2 Overall Response Rate and Disease Control Rate

Overall response rate (ORR) is defined as the proportion of patients with objective evidence of complete response (CR) or partial response (PR). The evaluation of ORR will be based on central independent review of the images (local CT image assessment and collect CT scans for central independent review).

CCI

At the analysis stage, the best overall response will be assigned for each patient as the best response recorded after initiation of study treatment. If applicable, responses recorded after disease progression or initiation of new anti-cancer treatment will be excluded.

The assessment of disease control rate (DCR) will parallel that of ORR, with DCR defined as the proportion of patients with objective evidence of complete response (CR), partial response (PR), or stable disease (SD).

### 6.2.2.3 Duration of Response

Duration of response is derived for those patients with objective evidence of PR or CR. DR (in months) is defined as the time from the first documentation of response (CR or PR) to the first documentation of objective tumor progression or death due to any cause: (date of first progression or death – date of first CR or PR +1)/30.4375.

Patients who are alive and progression free as of the analysis cut-off date will be censored at their last evaluable tumor response assessment before initiation of any new anti-cancer cancer treatment. Refer to **Table 4** for censoring rules for duration of response.

**Table 4 – Censoring Rules for Duration of Response**

Situation	End Date	Censored
Documented radiological PD	Date of the first tumor assessment that determined PD	No
Death during the study before PD	Date of death	No
Patients still followed without radiologic PD as of cut-off date	Date of last adequate tumor assessment prior to cut-off date	Yes
Non-study anti-cancer treatment initiated before radiologic PD	Date of last adequate tumor assessment prior to initiation of non-study anti-cancer treatment	Yes
Death or radiologic PD after a missed (or not available/not evaluable) tumor assessment	Date of last adequate tumor assessment prior to missed tumor assessment  A response assessment is considered missed if more than 13 weeks (91 days) has elapsed since the last image-based response assessment. If a patient develops progressive disease or dies after this interval, the tumor response assessment will be excluded from the analysis and censored at the last evaluable assessment. However, if an adequate image-based response assigned as CR, PR, or SD is obtained after more than 13 weeks, then the tumor response assessment will not be excluded from the analysis as long as no other censoring events have occurred.	Yes
Only non-evaluable (NE) tumor assessments after CR or PR	Date of last adequate tumor assessment prior to NE tumor assessments	Yes
General Considerations:  Tumor response assessment dates will be assigned based on the date the image was performed, not the date the image was assessed.		

## Statistical Analysis Plan

[figure not shown]
Protocol No. TO-TAS-114-201

Last Revision Date: 29NOV2017

---

**Note:** Tumor response assessments will be considered “adequate” for analysis if they are assigned as CR, PR, SD, or PD and are not censored (e.g., obtained prior to initiation of non-study anti-cancer treatment).

Tumor response assessments obtained after initiation of non-study anti-cancer treatment (systemic anti-cancer therapy, radiotherapy or cancer surgery) will not be included in the efficacy analyses, but will be flagged in the data listings. Tumor response assessments obtained the same day as initiation of non-study anti-cancer treatment will not be excluded.

### 6.3 Safety

Safety parameters that will be measured in the study are:

1. Adverse events
2. Laboratory measurements
3. Vital signs
4. ECG
5. Physical examination
6. ECOG performance status
7. Pregnancy test
8. Concomitant medications and therapies
9. Other diagnostics and procedures

#### 6.3.1 Study Day and Visit Window Definitions

The study windows listed in **Table 3** (based on visit dates) will be used to analyze physical examination, vital signs, height, weight, laboratory, ECOG and ECG measurements.

**Table 3 Safety Study Windows**

Visit	Safety Parameters	Target Day	Window
Baseline	Physical Examination, Vital Signs, Height, Weight, ECOG, Laboratory Measurements, ECG	Day -28 to Day 1	Day -28 to 1
Day 1 of Cycle 2 to 6	All	Day 1 of Cycle	Day -1 to 1 of Cycle
Day 1 of Cycle 7 and up	Laboratory Measurements	Day 1 of Cycle	Day -2 to 1 of Cycle
	Physical Examination, Vital Sign, Height, Weight, ECOG, ECG	Day 1 of Cycle	Day -1 to 1 of Cycle
Day 8 of all Cycles	All	Day 8 of Cycle	Day 2 to 11 of Cycle
Day 15 of Cycle 2 to 6	All	Day 15 of Cycle	Day 12 of Cycle to Day -2 of next Cycle
Day 15 of Cycle 7 and up	Laboratory Measurements	Day 15 of Cycle	Day 12 of Cycle to Day -3 of next Cycle
	Physical Examination, Vital Sign, Height, Weight, ECOG, ECG	Day 15 of Cycle	Day 12 of Cycle to Day -2 of next Cycle
End of Treatment	All	NA	No window will be used
30-Day Safety Follow-up	All	30 Days after Last Dose of Study Medication	Last Dose of Study Medication + 21 to Last Dose of Study Medication + 39 (i.e. +/- 9 days)

For post-baseline scheduled visits, the CRF visit will be used as analysis visit (i.e. no window will be used). Both scheduled and unscheduled assessments are included in the safety analyses. If more than one assessment is measured within the same visit window, the value closest to the target study day will be used for the analysis. If multiple values are the same number of days away from the target study day, then the latter value will be used. For Visit where time window is not applicable, the latest value would be used.

